3. STUDY DESIGN AND OBJECTIVES

Phase 2, open label, dose escalation study of two dose cohorts of bermekimab in patients with moderate to severe atopic dermatitis. The study is multicenter, and will consist of two dose levels: Bermekimab administered subcutaneously at a dose of 200 mg weekly (4 doses) and bermekimab administered subcutaneously at a dose of 400 mg weekly (8 doses). Patients taking the 200mg dose will be followed for 5 weeks (6 visits, day 35 ± 20 , and patients taking the 400mg dose will be followed for 8 weeks (9 visits, day 56 ± 20) to allow for assessment of safety and preliminary efficacy.

Dose escalation details can be found in Section 5.3.

The protocol of the study will be approved by the Institutional Review Board (IRB) or the Ethics Committee (EC) of the participating study sites. Depending on the participating countries, both local and central IRB/EC approvals will be granted. The study will be registered at www.clinicaltrials.gov before the enrollment of the first patient. The trial will be conducted in compliance with the protocol, GCP, and all applicable regulatory requirements.

3.1 STUDY ENDPOINTS

Primary Endpoint:

• Safety and Tolerability

Secondary Endpoints:

- Change in Eczema Area and Severity Index Score (EASI) from baseline to visit 8 EASI score will assess severity and extent of AD with respect to erythema, excoriation, infiltration and lichenification at 4 anatomic sites of the body: lower and upper extremities, trunk and head. The total EASI score shall be in a range (from 0 to 72 points (from no disease to maximum disease severity, respectively).
- Patients (%) achieving Investigator's Global Assessment (IGA) Response (0 or 1) at Visit
 - 8

IGA assesses disease severity and clinical response using a 5-point scale: 0 = clear; 1 = almost clear; 2 = mild; 3 = moderate; 4 = severe. The score is determined by ranking the extent of erythema and papulation/infiltration. A clinical response to therapy will be an IGA score of 0 (clear) or 1 (almost clear). Patients receiving more than one treatment with additional medication to treat AD exacerbation during the study or missing IGA scores at Visit 8 will be treated as non-responders.

- Patients (%) achieving ≥2 IGA Score Reduction at Visit 8
- Pharmacokinetics (PK) Assessment

An enzyme-linked immunosorbent assay (ELISA) has been developed to specifically measure bermekimab levels in human plasma. Blood will be drawn into a single 6 ml Na-Heparin collection tube at each PK collection time point (sample collection is pre-dose at visit 1, visit 3, visit 5, and visit 8). These samples will be collected per the study lab manual and immediately shipped to the Sponsor for PK analysis. The PK samples will also be used to test for the presence of antibodies against bermekimab.

- Change (%) for peak weekly averaged pruritus numerical rating scores (NRS) from baseline to visit 8
- The NRS rating system captures the intensity of patient's itch and pain over a 24-hour period. The following question will be presented to patients: "how would a participant rate his or her itch at the worst moment and on average during the previous 24 hours (scale 0 10 [0 = no itch; 10 = worst possible itch])?" and "how would you rate your pain on average during the previous 24 hours [0 = no pain; 10 = severe pain])?

```
CONFIDENTIAL
```

- Change in weekly averaged peak NRS from baseline to visit 8
- Change in SCORing Atopic Dermatitis (SCORAD) score from baseline to visit 8
 SCORAD was developed by the European Task Force on Atopic Dermatitis
 (Severity scoring of atopic dermatitis: the SCORAD index) as a measure of
 disease severity in AD. It includes assessment of the eczema in addition to patient
 reported symptoms. Total score ranges from 0 to 103 (no disease to most severe
 disease, respectively).
- Patients (%) achieving 50% or greater reduction in EASI Score from baseline to Visit 8
- Patients (%) achieving 50% or greater reduction in SCORAD Score to Visit 8
- Change (%) in Patient Oriented Eczema Measure (POEM) Scores from baseline to Visit 8
 POEM is a 7-item is a patient reported quality of life outcome measure based on a
 questionnaire to determine disease symptoms, including bleeding, cracking,
 dryness, flaking, itching, sleep loss and weeping. The scoring range is from 0 to
 28 (no disease to most severe disease, respectively).
- Changes in Global Individual Signs Score (GISS) from baseline to visit 8
 - GISS assesses AD lesions for erythema, excoriations, lichenification and edema/papulation. Each component will be rated on a global basis (over the entire body surface rather than by region) using a 4-point scale (0=none, 1=mild, 2=moderate and 3=severe) according to the EASI grading severity. Total score will range from 0 to 12 (no disease to most severe disease, respectively).
- Change from baseline to visit 8 in Dermatology Life Quality Index (DLQI)
- Change from baseline to visit 8 in Hospital Anxiety Depression Scale (HADS)
- Change (%) from pre- and post- injection of Visit 1 Questionnaire for pruritus, pain and erythema

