5.4 RESCUE TREATMENT(S)

If medically necessary (ie, to control intolerable AD symptoms), rescue treatment for AD may be provided to study patients at the discretion of the investigator. For the purpose of efficacy analysis, patients who receive rescue treatment during the study treatment period will be considered treatment failures, but they will continue study treatment if rescue consisted of topical medications. Topical calcineurin inhibitors may be used for rescue, but should be reserved for problem areas only, eg, face, neck, intertriginous and genital areas, etc. If possible, investigators should attempt to limit the first step of rescue therapy to topical medications, and escalate to systemic medications only for patients who do not respond adequately after at least 7 days of topical treatment. If a patient receives rescue treatment with systemic corticosteroids or non-steroidal systemic

immunosuppressive drugs (cyclosporine, methotrexate, mycophenolate-mofetil, azathioprine, etc.) study treatment will be immediately discontinued. Investigators should make every attempt to conduct efficacy and safety assessments (eg, disease severity scores, safety labs) immediately before administering any rescue treatment.

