10.5 STATISTICAL METHODS

All analyses will be summarized using descriptive statistics and data will be presented in tabular format for each treatment group and pooling all bermekimab dose groups together. Continuous data will be summarized for each treatment group using the number of observations available (N), means, standard deviation (SD), minimums, medians, and maximums. Categorical data will be summarized for each treatment group using counts and percentages. Missing data will not be categorized in the summaries.

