10.5.1 Handling Missing Data

If baseline assessment is not available, the baseline value will remain missing. The subject will not be included in baseline summaries.

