10.5.4 Efficacy Analysis

All primary and secondary efficacy analyses will be performed for SAF and PP populations. Summary statistics will be provided to evaluate the overall treatment effect and effect within the treatment group. No statistical comparison of differences will be performed across bermekimab dose groups.

Change from baseline to visit 8 will be summarized using descriptive statistics. Corresponding 95% confidence interval of the point estimate of mean change will be provided by treatment group and for overall pooled population. The number and percent of subjects achieving the response (as specified for the secondary endpoints) will be summarized by treatment groups and overall population along with 95% confidence interval for the point estimate. Number and percent of patients achieving response in EASI, and SCORAD core from baseline at visit 8, will be reported separately, along with 95% confidence interval for 50% or greater reduction.

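### A missing visit 8 score counts as non-response for IGA 0/1, but EASI-50 and SCORAD-50 have no such rule and no stated denominator, so their all-dosed rates can turn into completer rates

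*Combined protocol and SAP*

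**What the plan says.** Section 3.1 lists four responder endpoints at visit 8:

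- IGA 0/1. Its explanatory paragraph ends by saying that patients "missing IGA scores at Visit 8 will be treated as non-responders".
- "Patients (%) achieving ≥2 IGA Score Reduction at Visit 8", the next bullet, with no missing-data text of its own.
- "Patients (%) achieving 50% or greater reduction in EASI Score from baseline to Visit 8" (EASI-50), with no missing-data text.
- "Patients (%) achieving 50% or greater reduction in SCORAD Score to Visit 8" (SCORAD-50), with no missing-data text.

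The synopsis, Section 8.2 and Section 10 add nothing for the last three. The missing-data section, 10.5.1, deals with baseline alone: "If baseline assessment is not available, the baseline value will remain missing". Section 10.5 adds: "Missing data will not be categorized in the summaries". Section 10.5.4 promises counts, percentages and 95% confidence intervals, but no denominator: "The number and percent of subjects achieving the response (as specified for the secondary endpoints) will be summarized by treatment groups and overall population".

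Two other provisions bear on the point. Under 5.4, for efficacy purposes, "patients who receive rescue treatment during the study treatment period will be considered treatment failures". Under 10.3.1, the secondary endpoints are analysed in the safety set (SAF, everyone dosed) and in the per protocol set (PP, patients with both baseline and visit 8 disease assessments).

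**The concern.** The plan applies a conservative rule to one of four sibling endpoints and is silent on at least two others. Take a patient who withdraws without rescue and has no visit 8 scores. In the SAF that patient is a failure on IGA 0/1. On EASI-50 and SCORAD-50 the same patient may be counted as a failure or may leave the calculation, depending on how the programmer reads 10.5 and 10.5.4.

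If such patients are dropped, one table can carry an all-dosed IGA 0/1 rate beside completer rates for the other endpoints, under the same SAF label. The SAF results for those endpoints would then largely repeat the PP results, and the plan would have no all-dosed estimate for them.

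The study is open label, and Section 10 allows the analysis plan to be revised while the study runs. An unstated denominator could therefore be settled after responses are known.

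**Working it through.** **Inputs from the documents.** Group A has 9 patients and Group B has 20 (synopsis), 29 in all. Section 3 follows Group A for 5 weeks and 6 visits. The sample size is one of convenience (10.2), and the documents give no expected response or drop-out rate. There is thus no planned figure to reproduce.

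**Assumptions.** The number of responders r and the number d with no visit 8 score and no rescue are assumed, and shown as ranges.

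**Formulas.** With n dosed:

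- missing counted as non-response: r/n
- completers only: r/(n−d)
- ratio of the second to the first: n/(n−d), whatever r is
- gap: r·d / [n(n−d)]

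**Group B, n = 20, assumed r = 10.** The all-dosed rate is 10/20 = 50.0% (exact 95% CI 27.2 to 72.8) for every d.

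| d | Completer rate (exact 95% CI) | Ratio | Gap, points |
|---|---|---|---|
| 0 | 10/20 = 50.0% (27.2 to 72.8) | 1.00 | 0 |
| 1 | 10/19 = 52.6% (28.9 to 75.6) | 20/19 = 1.05 | 2.6 |
| 2 | 10/18 = 55.6% (30.8 to 78.5) | 20/18 = 1.11 | 5.6 |
| 4 | 10/16 = 62.5% (35.4 to 84.8) | 20/16 = 1.25 | 12.5 |
| 6 | 10/14 = 71.4% (41.9 to 91.6) | 20/14 = 1.43 | 21.4 |

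**Sensitivity to r, at d = 4.** With r = 6: 6/20 = 30.0% against 6/16 = 37.5%, a gap of 7.5 points. With r = 14: 14/20 = 70.0% against 14/16 = 87.5%, a gap of 17.5 points.

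**Overlap with PP.** A completer rate uses patients with baseline and visit 8 scores, which is how PP is defined. For unrescued patients who miss the whole visit 8 assessment, the SAF completer rate and the PP rate are the same number. They can differ only where a rescued patient without a visit 8 score is kept in the SAF as a failure under 5.4.

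**Group A.** If follow-up ends at visit 6, no Group A patient has a visit 8 score, so 9/29 = 31.0% of patients lack it by design. A literal visit 8 rule then gives Group A 0/9 (95% CI 0 to 33.6) and caps the pooled rate at 20/29 = 69.0%. Ten responders among the 20 in Group B would become 10/29 = 34.5% pooled. The existing IGA 0/1 rule already has this effect.

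**The case against.** The strongest reply is that the SAF is everyone dosed, 10.5.4 speaks of numbers and percentages of subjects, and 10.5 ties available observations to continuous data only. The remark that missing data are not categorized may mean no more than that tables carry no missing row. Because PP is already the completer analysis, a SAF that also dropped missing patients would be largely redundant, which argues against reading it that way. On the all-dosed reading the inflation is zero. This stands as a fair reading, but no sentence requires it, and the explicit rule for IGA 0/1 invites the inference that the other endpoints are handled differently.

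Several stronger readings are tempting, and the documents do not support them:

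- A reader might infer that rescued patients vanish from the rates. Section 5.4 makes them failures for efficacy generally, so only withdrawal or a missed visit without rescue is at issue.
- A reader might infer that three endpoints plainly lack the rule. The sentence refers to missing IGA scores at visit 8, so it could also cover the reduction of 2 points or more, although its place in the IGA 0/1 paragraph argues against that. The gap is clear for EASI-50 and SCORAD-50.
- A reader might infer that those who leave are mostly treatment failures. Section 5.5 also lists withdrawal of consent for any reason, pregnancy, detention and termination by the sponsor. It stops therapy and does not say that the visit 8 assessment is cancelled.
- A reader might infer that these rates are the declared basis for later trials. Section 1.2 says that of the dose-ranging study as a whole and names no responder rate.

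**Conclusion.** The point holds as an undefined denominator and missing-data rule for EASI-50 and SCORAD-50, with unclear reach to the IGA reduction of 2 points or more. It concerns the SAF analysis and patients who lack a visit 8 score without having been rescued. In PP the rule cannot act, because those patients are excluded.

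It would go too far to say that the rates will be inflated. The text permits a completer rate above the all-dosed rate and equally permits none. Under the completer reading, one to six missing patients out of 20 in Group B raise the rate by a factor of 1.05 to 1.43, or 2.6 to 21.4 points if there are 10 responders. Both counts are assumptions. With no missing patients the issue disappears.

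The endpoints are secondary and descriptive, and no decision threshold in the plan uses them, so this does not threaten the primary safety objective. It is still worth correcting: the sponsor has accepted the principle for IGA 0/1, and the documents give no reason to treat the sibling endpoints differently.

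**What to change.** First, reconcile the visit 8 endpoints with the 6-visit follow-up that Section 3 gives Group A, and state the endpoint visit for each group. Without this, extending the rule would make Group A non-responders by design.

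Then, in 3.1 and 10.5.4 (or once in 10.5.1), state one rule for IGA 0/1, IGA reduction of 2 points or more, EASI-50 and SCORAD-50. In the SAF analysis the denominator is every dosed patient in the group, and a patient with no score at that group's endpoint visit is a non-responder. Keep the observed-case rate as the PP result and label it as a completer analysis.

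The cost is a sentence or two for the rule, plus the reconciliation for Group A, which the existing IGA 0/1 rule needs anyway. No extra data are collected. The downside is that the reported SAF rates may be somewhat lower than on a completer reading.

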4. ELIGIBILITY CRITERIA

4.1 INCLUSION CRITERIA

No waivers/exemptions will be granted for protocol inclusion/exclusion criteria.

Subjects are included in the study if they meet all of the following criteria:

- Written informed consent provided by the patient
- Age ≥ 18 years
- Chronic Atopic Dermatitis present for at least 3 years
- Disease is not responsive to topical medications, or for whom topical treatments are not indicated or desired
- Willing and able to comply with all clinic visits and study-related procedure
- EASI score ≥ 16 at screening and baseline visits
- IGA score \geq 3 at screening and baseline visits
- $\geq 10\%$ body surface area (BSA) of AD involvement at screening and baseline visits
- Documented recent history (within 6 months before the screening visit) of inadequate response to treatment with topical medications or for whom topical treatments are otherwise medically inadvisable or undesired

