- 1. On a scale of 0 to 10, what is the current intensity of itch, with 0 being 'no itch' and 10 being the 'worst itch imaginable'.
- 2. On a scale of 0 to 10, what is the current intensity of pain, with 0 being 'no pain' and 10 being 'severe pain'.

The Investigator will assess the patient's Erythema and complete the following on the Visit 1 Questionnaire:

- 3. What is the current status of the patient's erythema overall?
- a. None \square Mild \square Moderate \square Severe \square
- b. Please describe area(s) and degree(s) of the patient's erythema in detail and if applicable any post-injection changes observed.

The Visit 1 Questionnaire will be performed twice:

- 1. Visit 1, pre-injection of bermekimab;
- 2. Visit 1, sixty minutes post-injection of bermekimab.

Patient Oriented Eczema Measure

The POEM is a 7-item, validated questionnaire used in clinical practice and clinical trials to assess disease symptoms in children and adults. The format is a response to 7 items (dryness, itching, flaking, cracking, sleep loss, bleeding, and weeping) based on frequency during the past week (ie, 0 = no days, 1 = 1 to 2 days, 2 = 3 to 4 days, 3 = 5 to 6 days, and 4 = every day) with a scoring system of 0 to 28; the total score reflects disease-related morbidity.

Hospital Anxiety and Depression Scale

The HADS is an instrument for screening anxiety and depression in non-psychiatric populations; repeated administration also provides information about changes to a patient's emotional state. The HADS consists of 14 items, 7 each for anxiety and depression symptoms; possible scores range from 0 to 21 for each subscale. The following cut-off scores are recommended for both subscales: 7 to 8 for possible presence, 10 to 11 for probable presence, and 14 to 15 for severe anxiety or depression.

Dermatology Life Quality Index

The DLQI is a 10-item, validated questionnaire used in clinical practice and clinical trials to assess the impact of AD disease symptoms and treatment on QOL. The format is a simple response (0 to 3 where 0 is "not at all" and 3 is "very much") to 10 questions, which assess QOL over the past week, with an overall scoring system of 0 to 30; a high score is indicative of a poor QOL.

CONFIDENTIAL

22 August 2018

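### Percent change is the only stated metric for the Visit 1 Questionnaire, but it is arbitrary for the uncoded erythema rating and undefined for any itch or pain score of 0 before injection.

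*Combined protocol and SAP*

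**What the plan says.** The synopsis and section 3.1 give the endpoint in the same words: "Change (%) from pre- and post- injection of Visit 1 Questionnaire for pruritus, pain and erythema". No absolute-change version is listed beside it, although for the weekly averaged peak NRS both a percent and an absolute change are listed.

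Section 8.2 defines the items. The patient rates itch and pain at that moment, for example "On a scale of 0 to 10, what is the current intensity of pain", with 0 meaning none. The investigator answers "What is the current status of the patient's erythema overall" by ticking None, Mild, Moderate or Severe and adds a free-text description. No numbers are attached to the four boxes. "The Visit 1 Questionnaire will be performed twice", before and after the first injection.

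Section 4.1 sets entry floors for disease extent and severity, such as "EASI score ≥ 16 at screening and baseline visits", together with IGA of at least 3 and at least 10% body surface area. It sets none for itch or pain.

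In the statistical plan, section 10.5 summarizes continuous data by N, mean, SD, minimum, median and maximum, and categorical data by counts and percentages. Section 10.5.1 deals only with an unavailable baseline. Section 10.5.4 describes change only from baseline to visit 8. None of these sections gives codes for erythema, a rule for a pre-injection score of 0, or an analysis of this within-visit comparison.

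**The concern.** Percent change needs a numeric scale and a non-zero starting value. The erythema item has no numeric scale in the plan, so whoever programs the table must choose one, and the choice changes the result. Even with agreed codes, dividing one ordinal rating by another treats the steps as equal and the lowest code as a true zero.

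For itch and pain the scale is numeric, but 0 is a permitted answer and the eligibility criteria do not rule it out. A single rating of the present moment is also more exposed to zeros than a weekly average. Scores just above 0 raise a second problem: a change of a few points becomes several hundred percent and can outweigh the rest of a small group.

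At stake is whether the symptom change after the first dose can be reported as stated, for every patient, and in a way that two analysts would reproduce.

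**Working it through.** The plan has no figure of its own to reproduce: section 10.2 calls the sample size one of convenience. The formula throughout is percent change = 100 × (post - pre) / pre.

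**Erythema (categories from section 8.2; both codings are illustrations).**

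| Transition | Codes 0-3 | Codes 1-4 |
|---|---|---|
| Severe to Moderate | (2-3)/3 = -33.3% | (3-4)/4 = -25.0% |
| Moderate to Mild | (1-2)/2 = -50.0% | (2-3)/3 = -33.3% |
| Mild to None | (0-1)/1 = -100% | (1-2)/2 = -50.0% |
| None to Mild | undefined | (2-1)/1 = +100% |

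The same observed transition gives a different endpoint value under each coding.

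**Itch and pain, zero before injection.** With pre = 0 the formula divides by zero. The proportion p scoring 0 on an item is not in the documents and is assumed here. With n = 9 (Group A), 20 (Group B) and 29 (total, synopsis), the expected number undefined is n × p, and the chance of at least one is 1 - (1 - p)^n.

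| Assumed p | Expected of 29 | n = 9 | n = 20 | n = 29 |
|---|---|---|---|---|
| 1% | 0.3 | 9% | 18% | 25% |
| 5% | 1.5 | 37% | 64% | 77% |
| 10% | 2.9 | 61% | 88% | 95% |
| 20% | 5.8 | 87% | 99% | 99.8% |

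**Itch and pain, low but non-zero before injection (invented scores).** A patient going from 8 to 6 changes by -25%, or -2 points. A patient going from 1 to 4 changes by +300%, or +3 points.

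- Nine patients, eight of the first kind and one of the second: mean percent change = (8 × -25 + 300)/9 = +11.1%; mean absolute change = (8 × -2 + 3)/9 = -1.44 points.
- Twenty patients, nineteen and one: (19 × -25 + 300)/20 = -8.75%, against (19 × -2 + 3)/20 = -1.75 points.
- Twenty patients, eighteen and two: (18 × -25 + 600)/20 = +7.5%, against (18 × -2 + 6)/20 = -1.5 points.

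One patient can reverse the sign of the mean in a group of 9, and two can in a group of 20.

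**The case against.** The best defense is that the general rules already do much of the work. Section 10.5 would tabulate erythema as counts and percentages in each category before and after injection. It also reports N and the median, so a reduced N would be visible, and in the examples above the median stays at -25%. The only none-to-severe coding in the protocol that names erythema is the 0-3 scale of the GISS, which the sponsor may have meant to reuse. A pre-injection erythema rating of None is unlikely, because entry requires IGA of at least 3 and section 3.1 bases the IGA partly on erythema. The percent sign might also mean the percentage of patients who changed.

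Part of this stands. The median limits the damage, and for erythema the main problem is the coding, not zeros. The rest does not close the gap. Separate category counts do not show individual shifts and do not yield a percent change. Nothing links the GISS codes to this questionnaire. Where the protocol means a percentage of patients, it says so in the endpoint name.

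A reader might infer three stronger things, and the documents support none of them:

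- That some patients will certainly have undefined values. The documents give no rate of zeros.
- That leaving out the zeros biases the result toward improvement. Patients at 0 cannot improve but may stay at 0, and no text says that they are dropped. Low non-zero scores pull the mean toward worsening, so the net direction is unknown.
- That worsening from 0 would go unseen as a safety signal. Both raw scores are collected, the erythema item asks for post-injection changes, and sections 5.1, 5.2 and 9.3 provide for injection-reaction monitoring and adverse event recording after the injection. Section 7 does not list this questionnaire among the safety measures.

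**Conclusion.** The concern holds as a defect in the endpoint definition. For erythema, the stated metric has no unique value: the transitions in the table that are defined under both codings differ by about 8 to 50 percentage points. For itch and pain, the metric fails at a permitted score and is unstable near it.

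The coding and division problems follow from the protocol's text alone. How often a zero would occur rests on the assumed rate: at 5% to 20% per item, at least one undefined value among 29 patients has a chance of about 77% to 99.8%; at 1% it is 25%. The sign reversals are constructed examples of what the metric allows, not predictions.

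The consequence is modest. This is one descriptive secondary endpoint in an uncontrolled study, with no formal test of the primary endpoint and no comparison between dose groups, and neither the escalation rules (section 5.3) nor the stopping rules (section 5.6) use it. It should still be corrected, because the replacement is better defined and uses the same data.

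**What to change.** In the synopsis, section 3.1 and section 10.5.4:

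- **Itch and pain:** make absolute change in points, from pre- to post-injection at Visit 1, the summary, including every patient with both ratings.
- **Erythema:** replace percent change with a pre/post shift table and give the number and percent improved, unchanged and worsened.
- **If percent change is kept for itch and pain:** make it supplementary and report how many patients were excluded for a pre-injection score of 0.
- **Section 10.5.4:** name this within-visit comparison, since the present text covers only change to visit 8.

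The cost is a small wording change to the protocol and the statistical plan. Because the endpoint is worded in the protocol itself, this may need an amendment. The questionnaire, its timing and the data collected stay as they are.
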